### 1.2.2.2 Study MET54 (Phase II)

MET54 was a Phase II, randomized, open-label, active-controlled, multi-center study conducted in Europe (Finland) in 2015. This study evaluated the immunogenicity and safety profile of a single dose of MenACYW conjugate vaccine when given alone in healthy, meningococcal-vaccine naïve toddlers compared to that of the licensed vaccine Nimenrix®. A total of 200 meningococcal vaccine naïve subjects aged 12 to 23 months on the day of enrollment were randomized to 1 of 2 groups. Group 1 received a single dose of MenACYW conjugate vaccine and Group 2 received a single dose of Nimenrix®.

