#### *hSBA*

Most subjects in both groups had hSBA titers  $\geq 1:8$  at D30: the percentages after MenACYW conjugate vaccine for serogroups A, Y, and W (ranging from 97.8% [89/91] to 98.9% [90/91]) were comparable to those after Nimenrix® (ranging from 91.9% [79/86] to 100.0% [86/86]). The percentage of subjects with hSBA titers  $\geq 1:8$  for serogroup C was higher after MenACYW conjugate vaccine (100.0% [91/91]) than after Nimenrix® (89.5% [77/86]). At D30, most subjects in both groups demonstrated an hSBA vaccine seroresponse. The percentage of subjects with an hSBA vaccine seroresponse for serogroups A, Y, and W was comparable in both groups (ranging from 96.7% [87/90] to 98.9% [90/91] after MenACYW conjugate vaccine and from 91.9% [79/86] to 98.8% [85/86] after Nimenrix®). The percentage of subjects with an hSBA vaccine seroresponse for serogroup C was higher after MenACYW conjugate vaccine (100.0% [91/91]) than after Nimenrix® (86.0% [74/86]).

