5.1.1.2 Statistical Methods

5.1.1.2.1 Statistical Method for Co-primary Objective 1

Each of the serogroups A, C, Y, and W will be tested separately. If the lower limit of the 2-sided 95% confidence interval (CI) of the difference between the 2 percentages is $> -10\%$, the inferiority assumption will be rejected.

For the 4 non-inferiority hypotheses using the response rates (percentages of subjects who achieve an hSBA titer $\geq 1:8$), the 95% CI will be stratified on the priming status (meningococcal vaccine naïve or primed monovalent MenC vaccination during infancy) and calculated using the Wald method (normal approximation). Weighted average of the difference over strata will be calculated using the Minimal Risk weights with the null variance method (2).

The 100(1- α)% two-sided CIs for the difference in proportions between two groups using the Minimum Risk Weights with the null variance are calculated as follows:

$$\hat{\delta}_w \pm Z_{\alpha/2} \sqrt{\left\{ \sum_{i=1}^s w_i^2 \hat{V}_0(\hat{\delta}_i) \right\}}$$

where $i=1,2, s=2, \hat{\delta}_w = \sum_{i=1}^s w_i \hat{\delta}_i = \sum_{i=1}^s w_i (\hat{P}_{iB} - \hat{P}_{iA}), \hat{P}_{iA}, \hat{P}_{iB}$ are the observed response rates for MenACYW vaccine group and the Nimenrix[®] group respectively at stratum $i, Z_{\alpha/2}$ is the 100(1-

$\alpha/2$)th percentile of the standard normal distribution, and w_i are the weight assigned at stratum i , and

$\hat{V}_0(\hat{\delta}_i) = \frac{\tilde{P}_{iA}(1-\tilde{P}_{iA})}{n_{iA}} + \frac{\tilde{P}_{iB}(1-\tilde{P}_{iB})}{n_{iB}}$ is the null variance, where $\tilde{P}_{iA}, \tilde{P}_{iB}$ are the constrained maximum likelihood estimates (MLEs) of response rates of MenACYW and Nimenrix at stratum i , and n_{iA}, n_{iB} are the sample sizes for MenACYW and Nimenrix at each stratum.

The Minimum Risk method computes the weights w_i as follows:

$$w_i = \frac{\beta_i}{\sum_{k=1}^s V_k^{-1}} - \left(\frac{\alpha_i V_i^{-1}}{\sum_{k=1}^s V_k^{-1} + \sum_{k=1}^s \alpha_k \delta_k V_k^{-1}} \right) \left(\frac{\sum_{k=1}^s \delta_k \beta_k}{\sum_{k=1}^s V_k^{-1}} \right)$$

where $\alpha_i = \delta_i \sum_{k=1}^s V_k^{-1} - \sum_{k=1}^s \delta_k V_k^{-1}$ and $\beta_i = V_i^{-1} \left(1 + \alpha_i \sum_{k=1}^s f_k \delta_k \right)$, $V_i = V(\hat{\delta}_i)$, and f_i is the fraction of subjects in the target population that belong in stratum i ($\sum_{i=1}^s f_i = 1$).

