For two strata, with observed values for V_i, f_i , and δ_i the formula reduces to the following:

$$\hat{w}_1 = \frac{\hat{V}_2 + \hat{f}_1(\hat{\delta}_1 - \hat{\delta}_2)^2}{\hat{V}_1 + \hat{V}_2 + (\hat{\delta}_1 - \hat{\delta}_2)^2}, \quad \hat{w}_2 = 1 - \hat{w}_1.$$

The overall non-inferiority of this objective will be demonstrated if all 4 individual null hypotheses are rejected.

5.1.1.2.2 Statistical Method for Co-primary Objective 2

Each of the serogroups A, C, Y, and W will be tested separately. If the lower limit of the 2-sided 95% CI of the difference between the 2 percentages is $> -10\%$, the inferiority assumption will be rejected.

For the 4 non-inferiority hypotheses using the response rates (percentages of subjects who achieve an hSBA titer $\geq 1:8$), the CI of the difference in proportions will be computed using the Wilson Score method without continuity correction (3).

Let $\hat{\theta} = p_1 - p_2$, then $L = \hat{\theta} - \delta$ and $U = \hat{\theta} + \varepsilon$ are respectively the lower and the upper limits of the CI, where:

$$\delta = Z_{0.025} \sqrt{\left\{ \frac{l_1(1-l_1)}{n_1} + \frac{u_2(1-u_2)}{n_2} \right\}}$$

$$\varepsilon = Z_{0.025} \sqrt{\left\{ \frac{l_2(1-l_2)}{n_2} + \frac{u_1(1-u_1)}{n_1} \right\}}$$

l_1 and u_1 are calculated from the CI of the single proportion in Group 1 given by:

$$\frac{(2n_1p_1 + Z_{0.025}^2 \pm Z_{0.025} \sqrt{(Z_{0.025}^2 + 4n_1p_1(1-p_1))})}{2(n_1 + Z_{0.025}^2)}$$

l_2 and u_2 are calculated from the CI of the single proportion in Group 2 given by:

$$\frac{(2n_2p_2 + Z_{0.025}^2 \pm Z_{0.025} \sqrt{(Z_{0.025}^2 + 4n_2p_2(1-p_2))})}{2(n_2 + Z_{0.025}^2)}$$

where $Z_{0.025}$ is the upper 97.5th percentile of the standard normal distribution.

The overall non-inferiority of this objective will be demonstrated if all 4 individual null hypotheses are rejected.

To conclude, non-inferiority in toddlers who either are meningococcal vaccine-naïve or have received monovalent MenC vaccination during infancy and non-inferiority in meningococcal vaccine-naïve subjects have to be demonstrated.

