5.1.2 Hypotheses and Statistical Methods for Secondary Objectives

5.1.2.1 Hypotheses

No hypotheses will be tested. Descriptive statistics will be presented.

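### SAP 5.1.1.2.1 prints the co-primary 1 difference as Nimenrix minus MenACYW, the reverse of its hypothesis and of the lower-limit rule

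*SAP*

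**What the plan says.** Protocol 12.1.1.1 and SAP 5.1.1.1.1 give the same co-primary 1 hypotheses: H0 is p(Men) − p(Nim) ≤ −10%, and H1 is that this difference exceeds −10%. The decision rule in SAP 5.1.1.2.1 begins "If the lower limit of the 2-sided 95% confidence interval (CI) of the difference between the 2 percentages is" and requires that limit to lie above −10%.

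The same section then gives the stratified estimator: "w_i (\hat{P}_{iB} - \hat{P}_{iA}), \hat{P}_{iA}, \hat{P}_{iB}$ are the observed response rates for MenACYW vaccine group and the Nimenrix[®] group respectively". The null-variance terms follow the same order: they "are the constrained maximum likelihood estimates (MLEs) of response rates of MenACYW and Nimenrix at stratum" i. The sample sizes `n_iA` and `n_iB` are also named MenACYW first, Nimenrix second. A is therefore MenACYW and B is Nimenrix throughout, and the stratum difference is B minus A.

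For co-primary 2, SAP 5.1.1.2.2 writes "Let $\hat{\theta} = p_1 - p_2", with 1 and 2 meaning Group 1 (MenACYW) and Group 2 (Nimenrix). That sign matches its hypothesis. Both co-primaries are needed for the claim: non-inferiority in the combined population and "non-inferiority in meningococcal vaccine-naïve subjects have to be demonstrated".

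**The concern.** The printed estimator and the hypothesis point in opposite directions, while the rule is one-sided. Reversing the difference and still asking for a lower limit above −10% puts the margin on the wrong vaccine. A MenACYW deficit appears as a positive difference and passes; a MenACYW advantage of about 10 points appears as a negative one and can fail.

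Co-primary 2 limits the damage but covers only Groups 1 and 2. Co-primary 1 is the only confirmatory test that includes the MenC-primed Groups 3 and 4. The primed-only comparison, secondary objective 3, concerns GMTs, and for the secondary objectives SAP 5.1.2.1 says "No hypotheses will be tested. Descriptive statistics will be presented".

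A second gap makes the intended direction harder to recover: the SAP does not state the value or direction at which the constrained MLEs are constrained.

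**Working it through.** The sample-size and power sections are redacted, so there is no figure in the plan to reproduce. The check substitutes the SAP's definitions into its formula and then measures the effect.

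**Sign.** With A = MenACYW and B = Nimenrix, δ_i = `P_iB − P_iA` = p(Nim) − p(Men) in stratum i. The hypothesis needs p(Men) − p(Nim).

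**Formulas (SAP 5.1.1.2.1 and 5.1.1.2.2).** For two strata, w1 = [V2 + f1(δ1 − δ2)²] / [V1 + V2 + (δ1 − δ2)²] and w2 = 1 − w1. The interval is Σw_iδ_i ± 1.96·√(Σw_i²V0_i). The weights do not change with the sign, because the differences enter only as a square.

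**Worked example.** Planned sizes are 306/306 naïve and 204/102 primed. A 10% loss (assumed) leaves 275/275/184/92. Assumed responders, MenACYW v Nimenrix: naïve 248/275 v 248/275; primed 110/184 v 83/92.

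- |δ1| = 0; |δ2| = 0.9022 − 0.5978 = 0.3043; (δ1 − δ2)² = 0.0926.
- V1 = 0.000644; V2 = 0.002266; f1 = 550/826 = 0.666 (naïve share).
- w1 = (0.002266 + 0.666 × 0.0926) / (0.000644 + 0.002266 + 0.0926) = 0.669; w2 = 0.331.
- Pooled difference = ±0.331 × 30.43 = ±10.1 points.
- Null variance, MLEs constrained at −10% in the direction of each difference: naïve 0.000734 both ways; primed 0.003661 as printed and 0.003073 corrected. Half-widths are 5.29 and 5.05 points.

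| Difference used | Estimate | 95% CI | Lower limit > −10%? |
|---|---|---|---|
| As printed, Nimenrix − MenACYW | +10.1 | +4.8 to +15.4 | pass |
| Corrected, MenACYW − Nimenrix | −10.1 | −15.1 to −5.0 | fail |

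Constraining at 0 instead gives +5.0 to +15.1 and −15.1 to −5.0, with the same decisions. For co-primary 2, the Wilson limits for 248/275 are 0.861 and 0.932, so the lower limit is −1.96·√(0.861 × 0.139/275 + 0.932 × 0.068/275) = −5.1 points: pass. As printed, both co-primaries pass despite a 30-point deficit in primed toddlers.

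**Co-primary 1 alone.** Simulated pass probability for one serogroup, planned sizes, same rates in both strata, 1,500 runs, MLEs constrained at −10%:

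| MenACYW v Nimenrix | As printed | Corrected |
|---|---|---|
| 80% v 90% (on the margin) | 1.000 | 0.025 |
| 75% v 90% | 1.000 | 0.000 |
| 99.5% v 89.5% | 0.023 | 1.000 |
| 90% v 90% | 0.998 | 0.999 |

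**Both co-primaries together.** One serogroup, 10% loss, 100,000 trials per scenario (Monte Carlo SE at most 0.16 points).

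- *Inferior in both strata.* Joint pass as printed is about 0% at 82% v 97% and about 2.5% at 87% v 97%, because co-primary 2 stops it.
- *Inferior in primed toddlers only* (naïve 90% v 90%, −10% constraint):

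| Primed, MenACYW v Nimenrix | As printed | Corrected |
|---|---|---|
| 60% v 90% | about 97% | about 2% |
| 65% v 90% | about 97% | about 9% |
| 70% v 90% | about 97% | about 28% |
| 75% v 90% | about 97% | about 58% |
| 80% v 90% | about 97% | about 84% |

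- *MenACYW better.* In the Phase II trial MET54 (Protocol 1.2.2.2) the percentage with hSBA ≥ 1:8 "for serogroup C was higher after MenACYW conjugate vaccine (100.0% [91/91]) than after Nimenrix ® (89.5% [77/86"]), but only "in healthy, meningococcal-vaccine naïve toddlers compared to that of the licensed vaccine". Taking 99.9% v 89.5% in naïve toddlers and assuming 99% v 99% in primed, the printed rule fails in 31–49% of trials depending on the variance used. It fails in 59% if the constraint stays at p(Men) − p(Nim) = −10%. The corrected rule fails in about 0%.
- *Loss rate.* From no loss to 15% loss (260/260/173/87), the 60% v 90% case passes 98% to 96% as printed and 2–3% corrected. The MenACYW-better case fails 28–44% at no loss and 33–51% at 15% loss.

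**The case against.** The strongest reply is that the intent is plain. Both documents state the hypotheses with named arms, the SAP introduces the interval as serving those hypotheses, and co-primary 2 is signed correctly. A programmer would have to ignore all of that in favour of one subscript order. This stands as an account of what probably happened: the SAP contradicts itself rather than consistently specifying the wrong test. It does not remove the error, because this section is the only place in either document that gives the co-primary 1 formula.

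The scenarios can also be called selective, and this partly stands. No document gives primed response rates, and 60% v 90% is extreme. At 80% v 90% the corrected rule still passes 84%. With naïve 98% v 98% and primed 85% v 99% it passes about 96–99%, against 100% as printed. Pooling the strata already gives limited protection against moderate primed-only inferiority, and the sign correction does not change that. The false-failure risk is likewise specific to serogroup C-like rates: at naïve 98% v 92% the printed rule fails only about 0.6–2.6%.

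A large primed deficit would also be visible in the planned descriptive tables of hSBA ≥ 1:8. That is true, but those tables are not confirmatory.

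On the constraint, reading the null variance as referring to H0 would supply the direction. That is reasonable, and it is a reason to say so in the text.

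Finally, the formula was read by program from a PDF. The arm order appears three times but the subtraction only once, so a misread is unlikely but not excluded.

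**Conclusion.** The concern holds, and it must be fixed. As written, the co-primary 1 interval is for Nimenrix minus MenACYW and does not test the stated hypothesis. The sign conflict follows from the text alone and rests on no assumed rate.

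The size of the consequence does rest on assumptions: the loss rate, the response rates (no primed rates are given), one serogroup and the unstated null-variance constraint. It is near zero when the vaccines are equal and is contained by co-primary 2 when MenACYW is inferior in both strata. It is large when inferiority is confined to primed toddlers, and material when MenACYW is about 10 points better in naïve toddlers. Nothing here shows that the program carries the wrong sign.

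**What to change.** In SAP 5.1.1.2.1, write the stratum difference as `P_iA − P_iB` with A = MenACYW and B = Nimenrix, or swap the A and B labels throughout the section. Keep the rule that the lower limit must exceed −10%. State the null-variance constraint in the same direction, `P_iA − P_iB` = −10%, which is the boundary of the SAP's own H0. This matters because the interval width depends on the direction of a −10% constraint, so reversing the sign of the printed interval does not give exactly the right limits. Then check the analysis program against p(Men) − p(Nim).

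The cost is a one-line SAP correction, one added phrase and a program check. No patients are needed, and the protocol needs no amendment because its hypothesis is already in the right direction.

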5.1.2 Hypotheses and Statistical Methods for Secondary Objectives

5.1.2.1 Hypotheses

No hypotheses will be tested. Descriptive statistics will be presented.

5.1.2.2 Statistical Methods

5.1.2.2.1 Statistical Method for Secondary Objective 1

Thirty days after the administration of MenACYW conjugate vaccine or Nimenrix[®] in toddlers who either are meningococcal vaccine naïve or have received monovalent MenC vaccination during infancy, the hSBA geometric mean titer ratio (GMTR) between MenACYW conjugate vaccine or Nimenrix[®] will be calculated, and 95% CI will be provided. The 95% CI of the ratio of post-vaccination GMTs will be stratified on the priming vaccination status (meningococcal vaccine naïve or primed monovalent MenC vaccination) and calculated using an analysis of variance (ANOVA) model of log₁₀-transformed titers.

5.1.2.2.2 Statistical Method for Secondary Objective 2

Thirty days after the administration of MenACYW conjugate vaccine or Nimenrix[®] in meningococcal vaccine naïve toddlers, the hSBA GMTR between MenACYW conjugate vaccine or Nimenrix[®] will be calculated, and 95% CI will be provided.

5.1.2.2.3 Statistical Method for Secondary Objective 3

Thirty days after the administration of MenACYW conjugate vaccine or Nimenrix[®] in toddlers who received monovalent MenC vaccination during infancy, the hSBA GMTR between MenACYW conjugate vaccine or Nimenrix[®] will be calculated, and 95% CI will be provided.

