## 5 Investigational Plan

### 5.1 Description of the Overall Trial Design and Plan

#### 5.1.1 Trial Design

This will be a Phase III, modified double-blind, randomized, parallel-group, active-controlled, multi-center trial to compare the immunogenicity and describe the safety of a single dose of MenACYW conjugate vaccine to a single dose of a licensed quadrivalent meningococcal polysaccharide groups A, C, W-135, and Y conjugate vaccine, Nimenrix®, in toddlers (12 to 23 months of age) in the EU who are either meningococcal vaccine naïve or received monovalent MenC vaccination during infancy.

Approximately 918 healthy toddlers aged 12 to 23 months will be enrolled and randomized as follows depending on the meningococcal background:

**Meningococcal Vaccine-Naïve Subjects:** 612 subjects will be randomized in a 1:1 ratio to the following 2 groups:

- Group 1: MenACYW conjugate vaccine (n=306)
- Group 2: Nimenrix® (n=306)

**MenC-Primed Subjects:** 306 subjects will be randomized in a 2:1 ratio to the following 2 groups:

- Group 3: MenACYW conjugate vaccine (n=204)
- Group 4: Nimenrix® (n=102)

Enrollment of MenC-primed subjects will be stratified by the type of primed vaccine, MenC-TT (NeisVac-C®) or MenC-CRM (Menjugate®, Meningitec®), considering that at least 25% and a maximum of 50% of subjects will have been primed with MenC-CRM as described in [Table 5.1](#).

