#### V01 (D0): Inclusion, Randomization, Blood Sample, and Vaccination

- 1) Give the subject's parent/legally acceptable representative information about the trial, answer any questions, obtain signed informed consent, and give him/her a signed copy.
- 2) Check inclusion and exclusion criteria for eligibility.
- 3) Take the subject's temperature (axillary, rectal, or oral, but axillary preferred) and record in the source document.
- 4) Collect demographic data.

- 5) Obtain verbal medical history about the subject.
- 6) Review vaccination history from the child's immunization record. For subjects who will be randomized to Group 3 or Group 4, record meningococcal vaccination history from the child's immunization record, including MenC vaccination history during infancy, the number of doses, the date(s) received, and the brand name of the product received.
- 7) Perform a physical examination, including but not limited to examination of the head (including ear, nose, and throat), neck, thorax (including heart and lungs), abdomen, and extremities. If a routine examination had been performed within the last month by the Investigator, a sub-investigator, or a licensed nurse practitioner, it does not need to be repeated unless there were some changes in health status, in which case it may be limited to the affected area.
- 8) Connect to the Interactive Web Response System (IWRS) for subject identification and randomization.
- 9) Obtain the first 5-milliliter (mL) blood sample (see [Section 7.1](#) for detailed instructions regarding the handling of blood samples).
- 10) Administer the appropriate study vaccine IM in the anterolateral area of the thigh or the deltoid muscle of the upper arm according to country specific recommendations and according to the study group listed below:
  - Group 1 and Group 3 = MenACYW conjugate vaccine
  - Group 2 and Group 4 = Nimenrix®
- 11) Keep the subject under observation for 30 minutes and record any AE in the source document.
- 12) Give the parent/legally acceptable representative a diary card, a thermometer, and a ruler, and go over the instructions for their use.
- 13) Remind the parent/legally acceptable representative to expect a telephone call (TC) 8 days (+2 days) after V01 (D0) and to bring back the DC when they return for V02 (D30 + 14 days).
- 14) Remind the parent/legally acceptable representative to notify the site in case of an SAE.
- 15) Complete the relevant CRF pages for this visit.

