## 6.5 Randomization and Allocation Procedures

Each 12 to 23 month old toddler whose parent/legally acceptable representative signs the ICF, and who meets the inclusion/exclusion criteria will be randomly assigned via IWRS to Group 1 and Group 2 for the meningococcal vaccine-naïve subjects according to a 1:1 ratio and to Group 3 and Group 4 for the MenC-primed subjects according to a 2:1 ratio. Site staff will connect to the IWRS, enter the identification and security information, and confirm a minimal amount of data in response to IWRS prompts. The IWRS will then provide the group assignment and have the caller confirm it. The full detailed procedures for group allocation are described in the Operating Guidelines. If the subject is not eligible to participate in the trial, the information will only be recorded on the subject recruitment log.

Subject numbers that are assigned by the IWRS will consist of an 8-digit string (a 3-digit trial center identifier and a 5-digit subject identifier connected by "-"). For example, Subject 001-00001 is the first subject enrolled in center number 1. Subject numbers should not be reassigned for any reason.

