### 7.1 Sample Collection

At Visits 1 and 2, 5 mL of blood will be collected by staff experienced in blood collection in a pediatric population in tubes provided by or recommended by the Sponsor. Immediately prior to the blood draw, the staff member performing the procedure will verify the subject’s identity; will verify the assigned subject’s number on the pre-printed label that contains that subject’s number and the sampling stage; and will attach the label to the tube. Blood is to be taken from the limb opposite to the one that will be used for vaccination.

If attempts to obtain the first blood draw are unsuccessful (after reasonable attempts as per local regulations) then Visit 1 can be rescheduled to a later date at which point inclusion/exclusion criteria must be re-validated. If during the rescheduled visit the first blood draw cannot be obtained, the subject will be withdrawn from the study without being vaccinated.

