#### 9.2.1.2 Immunogenicity Assessment Methods

##### *Antibodies to meningococcal antigens (hSBA method)*

The immunogenicity hSBA assessment method for the secondary endpoints is the same as the method presented in [Section 9.1.1.2](#).

This method will be performed on all blood samples (BL1 and BL2) for all study groups.

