#### **12.1.2.1 Secondary Objective 1**

Thirty days after the administration of MenACYW conjugate vaccine or Nimenrix® in toddlers who either are meningococcal vaccine naïve or have received monovalent MenC vaccination during infancy, the hSBA geometric mean titer ratio (GMTR) between MenACYW conjugate vaccine or Nimenrix® will be calculated, and 95% CI will be provided. The 95% CI of the ratio of post-vaccination GMTs will be stratified on the priming vaccination status (meningococcal vaccine naïve or primed monovalent MenC vaccination) and calculated using an analysis of variance (ANOVA) model of log10-transformed titers.

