#### **12.1.2.3 Secondary Objective 3**

Thirty days after the administration of MenACYW conjugate vaccine or Nimenrix® in toddlers who received monovalent MenC vaccination during infancy, the hSBA GMTR between MenACYW conjugate vaccine or Nimenrix® will be calculated, and 95% CI will be provided

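### The descriptive hSBA GMT ratios adjust for neither the day 0 titre nor the MenC carrier type; a supportive ANCOVA is an optional precision gain, most plausible for serogroup C in primed toddlers

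*SAP*

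**What the plan says.** Protocol 12.1.2 and SAP 5.1.2.2 plan three day 30 hSBA GMT ratios between the vaccines, each with a 95% CI and no hypothesis test.

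- Objective 1 (naïve and primed together): in Protocol 12.1.2.1 the interval is stratified on "priming vaccination status (meningococcal vaccine naïve or primed monovalent MenC vaccination) and calculated using an analysis of variance (ANOVA) model" of log10 titres, and SAP 5.1.2.2 has the same two classes, "vaccine naïve or primed monovalent MenC vaccination) and calculated using an analysis of variance (ANOVA) model". No day 0 term is named.
- Objective 2 (naïve): no model or covariate is named.
- Objective 3 (primed): the plan gives, "in toddlers who received monovalent MenC vaccination during infancy, the hSBA GMTR between MenACYW conjugate vaccine or Nimenrix" and a 95% CI. No model or covariate is named.

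Both candidate covariates are collected. On the hSBA assay, Protocol 9.2.1.2 says "This method will be performed on all blood samples (BL1 and BL2) for all study groups". At Visit 1, sites record for primed subjects the meningococcal history, "including MenC vaccination history during infancy, the number of doses, the date(s) received, and the brand name of the product received" (Protocol 5.1.4), which identifies the carrier.

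The plan does use this information elsewhere. It reports day 0 GMTs, the percentage with a 4-fold rise and hSBA seroresponse (SAP 4.4.2 and 5.1.3.2), and it describes responses by carrier type under the observational objectives (Protocol 5.1.2, SAP 2.3).

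**The concern.** A baseline titre that correlates with the day 30 titre explains part of the residual variance. Leaving it out keeps the ratio unbiased but may make its interval wider than necessary, and a chance baseline difference between arms then passes into the estimate. The planned day 0 GMTs would show such a difference but would not adjust the ratio for it. The fold-rise and seroresponse results refer to baseline, but they are not adjusted GMT ratios. The same argument applies to carrier type if the two priming vaccines lead to different day 30 titres.

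Objective 3 is where absolute width matters most: it compares 204 with 102 toddlers, the smallest of the three comparisons. At stake is the precision of descriptive ratios. No margin, power figure or co-primary conclusion depends on them.

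**Working it through.** There is no planned figure to reproduce: the documents state no precision for the GMT ratios, and the sample-size sections are redacted. The inputs from the documents are the planned group sizes, 306/306 naïve and 204/102 primed (Protocol 5.1.1), and the rule that values below LLOQ are set to LLOQ/2 (SAP 5.3.2). Assumed inputs are a log10 SD of 0.5, the correlation r between day 0 and day 30 titres within arm and priming stratum, the share of day 0 titres below LLOQ, and the carrier gap.

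**Baseline titre, no values below LLOQ.** Narrowing of the log-scale interval = 1 − √(1 − r²).
- r 0.1: 1 − √0.99 = 0.5%
- r 0.3: 1 − √0.91 = 4.6%
- r 0.5: 1 − √0.75 = 13.4%

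The relative gain is the same for all three objectives. For absolute width, the interval is the ratio multiplied and divided by 10^(1.96 × 0.5 × √(1 − r²)/√S), where S is the sum over strata of n1·n2/(n1 + n2). This gives 153 for naïve, 68 for primed and 153 + 68 = 221 for both.

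| Objective | S | r 0 | r 0.3 | r 0.5 |
|---|---|---|---|---|
| 1 | 221 | 1.164 | 1.156 | 1.140 |
| 2 | 153 | 1.200 | 1.190 | 1.171 |
| 3 | 68 | 1.315 | 1.298 | 1.267 |

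**Baseline titre, many values below LLOQ.** These figures come from simulation at the planned sizes, with floored values coded LLOQ/2. Each is the mean percentage by which the standard error of the vaccine effect falls. The correlation is the one before flooring, and the floor share is the same in every stratum.

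| Share below LLOQ | Objective | r 0.1 | r 0.3 | r 0.5 |
|---|---|---|---|---|
| 80% | 1 | 0.2 | 2.3 | 6.8 |
| 80% | 2 | 0.2 | 2.3 | 6.7 |
| 80% | 3 | 0.1 | 2.2 | 6.5 |
| 95% | 1 | 0.0 | 1.0 | 2.8 |
| 95% | 2 | 0.0 | 0.9 | 2.7 |
| 95% | 3 | −0.1 | 0.9 | 2.6 |

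If, in addition to 95% below LLOQ, 30% of day 30 titres sit at ULOQ, objective 2 gains 0.0 / 0.5 / 1.2%.

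**Which serogroups.** Primed toddlers received monovalent C vaccine, and other meningococcal vaccines are excluded (Protocol 5.2.4 and 5.2.5). For A, Y and W the documents therefore give no vaccine-related reason for primed baselines to differ from naïve ones, and a common floor share is the natural assumption. For serogroup C a lower floor share in primed toddlers is plausible. At the extreme of none floored, objective 3 takes the no-floor figures. Objective 1 then gains 0.3 / 2.9 / 8.6% with 80% of naïve baselines below LLOQ, or 0.2 / 2.0 / 5.7% with 95%.

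**Carrier type alone, objective 3.** Narrowing = 1 − √(0.25/(0.25 + p(1 − p)d²)), where 0.25 is the within-carrier variance (0.5²), p the MenC-CRM share and d the log10 gap in day 30 titre. Protocol Table 5.1 gives p from 52/204 = 25.5% to 50%.
- d = 0: none
- d = 0.1: 0.4% to 0.5%
- d = 0.3: 3.3% to 4.2%

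**Cost of missing day 0 titres.** If a share m of subjects drops out of the ANCOVA and the narrowing is g, the net width is (1 − g)/√(1 − m) of the planned width. Break-even is m = 1 − (1 − g)².
- No floor: break-even m = r², that is 1 / 9 / 25%. With m = 2% the net narrowing is −0.5 / 3.6 / 12.5%.
- 95% below LLOQ (objective 2): break-even is about 0.1 / 1.8 / 5.3%. With m = 2% the net narrowing is about −1.0 / −0.1 / +1.7%.

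**The case against.** The strongest reply is that this is a preference. The ratios are descriptive (SAP 5.1.2.1), randomisation within priming status makes them unbiased, and the plan already has baseline-referenced results and results by carrier. All of that stands and is why this is no more than an optional improvement. What remains is that none of those outputs is an adjusted between-vaccine GMT ratio.

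The second reply is that the gain may be negligible. It is plausible, though not documented, that most naïve toddlers, 612 of 918 subjects, start below LLOQ. A few missing day 0 results could then make the ANCOVA interval slightly wider than the planned one. This also stands. Protocol 7.1 secures the blood draw ("If during the rescheduled visit the first blood draw cannot be obtained, the subject will be withdrawn from the study without being vaccinated") but not a valid titre for each serogroup, and FAS and PPAS validity rest on the post-vaccination result (SAP 5.2.1 and 5.2.2).

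A reader might also infer that the analysis ignores a randomisation stratum. The protocol says "Enrollment of MenC-primed subjects will be stratified by the type of primed vaccine", and the planned counts in Table 5.1 keep 2:1 within each carrier type. But Protocol 6.5 describes allocation only as "to Group 3 and Group 4 for the MenC-primed subjects according to a 2:1 ratio" and leaves the details to the Operating Guidelines. Carrier type is therefore documented as an enrolment stratum, and the case for including it is prognostic only.

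Finally, the change is late. The SAP describes enrolment and the statistical data review in the past tense (SAP 3.1, 3.2 and 5.6).

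**Conclusion.** The point holds as an optional gain in precision of low priority. The documents do not support reading the omission as an error, a bias or a threat to the co-primary conclusions. Nor do they support 13% as the expected gain, since that needs both r = 0.5 and no baseline below LLOQ. With 80% to 95% of baselines below LLOQ in all strata, the gain at r = 0.3 is about 1% to 2.3%, and at r = 0.5 about 2.8% to 6.8%. Objective 3 gains most in absolute width, but a larger relative gain there would need a higher correlation or fewer floored baselines in primed toddlers. This is plausible for serogroup C but not shown in the documents. Carrier type adds little unless the day 30 gap is near 0.3 log10. The formulas are firm; all sizes rest on the assumed SD, correlation, floor share and carrier gap.

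**What to change.** In SAP 5.1.2.2, with an entry in SAP 5.7 (now marked not applicable), add a supportive ANCOVA of log10 day 30 titre on vaccine and log10 day 0 titre. For objective 1 add a three-level factor (naïve, MenC-TT, MenC-CRM); for objective 3 add MenC-TT versus MenC-CRM. Keep the unadjusted protocol ratio beside it, because that ratio also covers subjects without a valid day 0 result. Report the number of subjects in each analysis and the share of day 0 titres below LLOQ by serogroup, so that the reader can see where adjustment could help.

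The cost is a documented change to a descriptive analysis and a little programming, with no new visit, sample or assay. Protocol 6.4 keeps the sponsor blinded until database lock, so the model can still be fixed blind if lock has not occurred. Otherwise it should be labelled post hoc.
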